PROTOCOL TITLE

Open-Label Prospective Randomized Control Trial to Investigate the Efficacy of Omega-3 Fatty Acid Therapy in Preventing Gastrointestinal Bleeding in Patients with Continuous-Flow Left Ventricular Assist Device

Version: 05Jun2019

NCT03784963

PROTOCOL TITLE

Open-Label Prospective Randomized Control Trial to Investigate the Efficacy of Omega-3 Fatty Acid Therapy in Preventing Gastrointestinal Bleeding in Patients with Continuous-Flow Left Ventricular Assist Device

PRINCIPAL INVESTIGATOR

[name]
Department of Medicine, Section of Cardiology
[contact]

OBJECTIVES

Aim 1: We will evaluate whether high-dose omega-3 fatty acid (O3FA) supplementation alters markers of angiogenesis and inflammation in patients with continuous-flow left ventricular assist devices (CF-LVAD).

- **Aim 1a** will assess the effect of high-dose O3FA in patients who have not experienced an episode of gastrointestinal (GI) bleeding. Patients will be enrolled up to 3 months following CF-LVAD implantation and randomized to high-dose O3FA or none. Markers of angiogenesis and inflammation will be assessed prior to and following initiation of high-dose O3FA therapy.
- **Aim 1b** will assess the effect of high-dose O3FA in CF-LVAD patients who have already experienced a GI bleeding event. Patients who have experienced a prior bleeding event will be enrolled and randomized to high-dose O3FA or none. Markers of angiogenesis and inflammation will be assessed prior to and following initiation of high-dose O3FA therapy.

Aim 2: We will assess the changes that occur to the microbiome of CF-LVAD patients following O3FA supplementation.

Aim 3: We will assess the effect of high-dose O3FA supplementation on GI bleeding events in both the population without prior GI bleeding events, and the population with prior GI bleeding events.

BACKGROUND

Continuous-flow left ventricular assist devices (CF-LVAD) have become the mainstay of therapy for advanced heart failure, both as bridge to transplantation and as destination therapy, allowing significant improvement in survival. However, this therapy is limited by a high adverse event profile, specifically those related to hemocompatibility.

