One of the leading causes for readmission after CF-LVAD implantation is gastrointestinal (GI) bleeding, representing nearly 30% of both early and late readmissions following device implantation¹. Multiple reports found that 25-40% of the patients will experience GI bleeding, with 15.9% in the first 6 months in the MOMENTUM 3 trial, and 35.1% in the ENDURANCE trial^{2, 3}. Originally, pathophysiology of GI bleeding was attributed to Von Willebrand factor deficiency^{4, 5}. More recently, focus has shifted to the development of arteriovenous malformations (AVMs) in the GI tract as a major contributor to the development of GI bleeding in patients supported with CF-LVADs⁶.

The process of angiogenesis is controlled by angiopoietins 1 and 2 (Ang-1 and Ang-2), and vascular endothelial growth factor (VEG-F). Ang-1 leads to normal angiogenesis in conjunction with VEG-F, while Ang-2 promotes dysfunctional vessel growth with an expression that is highly regulated by the thrombin receptor PAR-1. Our group recently demonstrated that an abnormal ratio of Ang-1 and Ang-2 has a key role in abnormal angiogenesis, due to elevated Ang-2 and reduced Ang-1⁷. CF-LVAD patients with Ang-2 levels above the mean had more nonsurgical bleeding events compared to those with levels below the mean⁷. Furthermore, we found that tumor necrosis factor- α (TNF- α) was significantly higher in serum of patients with CF-LVAD compared to patients with heart failure or heart transplantation, and contributes to abnormal angiogenesis by killing pericytes and reducing Ang-1 levels⁸. We have confirmed these findings in a larger cohort from the PREVENT biobank. 114 paired samples obtained before and 3 months after CF-LVAD implantation were analyzed. 69% of patients with increased levels of Ang-2 and TNF- α experienced significant GI bleeding 6 months after implantation while only 38% of patients with Ang-2 and TNF- α levels below the mean had GI bleeding ($p=0.02$).

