The data presented thus far shows a possible link between O3FA, GI bleeding, and abnormal angiogenesis, and may be related to the microbiome in CF-LVAD patients. This prospective randomized study aims to evaluate the effect of supplemental O3FA on the frequency of GI bleeding in patients implanted with CF-LVAD both as primary and secondary prevention.

Additionally, we will investigate the effect of O3FA on angiogenesis parameters (Ang-1, Ang-2, VEGF, TNF- α) and the microbiome.

STUDY ENDPOINTS

The primary endpoint will be a change in angiogenesis markers resulting in dysregulated angiogenesis, as described above. Secondary endpoints include rate of GIB and improvement in inflammatory markers.

STUDY INTERVENTION

The study intervention being evaluated is high-dose O3FA (4,000 mg), which is an over-the-counter supplement. Heart failure patients are routinely instructed to take an O3FA supplement for heart health. The research team will fund the supplement, which will be stored in the heart failure office. Once a patient is enrolled, a total of 1 year of supplement will be given to the patient for consumption at home.

PROCEDURES INVOLVED

We will perform an open-label, prospective, randomized control study in which 120 CF-LVAD patients are enrolled. We plan to have 2 separate arms: primary prevention and secondary prevention (60 in each arm). In the primary prevention arm, 60 patients who have received CF-LVAD implantation and have not experienced any episodes of GI bleeding will be assigned to an O3FA group or a control group, with 30 patients in each group. In the secondary prevention arm, 60 LVAD patients who have experienced at least 1 episode of GI bleeding after CF-LVAD implantation will be assigned to an O3FA group or a control group, with 30 patients in each group. Randomization will be performed using computer software, and initiation of therapy will start within 24 hours of randomization. O3FA will be given at a dose of 4,000 mg orally per day, and all patients will receive guideline-directed medical therapy during the study period.

The following study procedures will be performed:

Baseline

Subject to sign consent
Verify inclusion/exclusion criteria
Record medical history and medications
Collect stool sample
Collect blood sample
Randomization
For O3FA subjects:
-Provide O3FA supplement
-Subjects will be instructed to take 4 pills a day

1.5 months post-randomization

Record medical history and medications
Record adverse events

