For O3FA subjects:
-Provide O3FA supplement
-Subjects will be instructed to take 4 pills a day
-Study drug compliance check

3 months post-randomization

Record medical history and medications

Collect stool sample

Collect blood sample

Record adverse events

For 03FA subjects:

- Provide O3FA supplement

- Subjects will be instructed to take 4 pills a day

- Study drug compliance check

4.5 months post-randomization

Record medical history and medications

Record adverse events

For 03FA subjects:

- Provide O3FA supplement

- Subjects will be instructed to take 4 pills a day

- Study drug compliance check

6 months post-randomization

Record medical history and medications

Collect stool sample

Collect blood sample

Record adverse events

For 03FA subjects:

- Provide O3FA supplement

- Subjects will be instructed to take 4 pills a day

- Study drug compliance check

7.5 months post-randomization

Record medical history and medications

Record adverse events

For 03FA subjects:

- Provide O3FA supplement

- Subjects will be instructed to take 4 pills a day

- Study drug compliance check

9 months post-randomization

Record medical history and medications

Record adverse events

For 03FA subjects:

- Provide O3FA supplement

- Subjects will be instructed to take 4 pills a day

- Study drug compliance check

10.5 months post-randomization

Record medical history and medications

Record adverse events

For 03FA subjects:

- Provide O3FA supplement

- Subjects will be instructed to take 4 pills a day

- Study drug compliance check

1 year post-randomization

Record medical history and medications

Collect stool sample

Collect blood sample

Record adverse events

For O3FA subjects:

-No more O3FA supplements will be provided by the study

-Study drug compliance check

Stool Collection for Microbiome Sequencing Analysis

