Complete metabolic panel including liver function tests, complete blood count, lipid profile, and inflammatory markers (hs-CRP and ESR) will be collected as standard of care. Approximately 20mL of peripheral blood will be collected and tested for markers of angiogenesis using a multiplex immunoassay system (Biorad). The angiogenesis factors to be measured are angiopoietin-2, epidermal growth factor (EGF), endoglin, sCD40L, vascular endothelial growth factor A, C and D, (VEGF-A, -C, -D), placental growth factor (PIGF), heparin-binding EGF-like growth factor (HB-EGF), plasminogen activator inhibitor-1 (PAI-1), insulin-like growth factor binding protein (*IGFBP*)-1, transforming growth factor alpha (TGF- α), and urokinase-type plasminogen activator (uPA). The inflammatory markers to be measured are Interleukin-6 (IL-6), Interleukin-8, Interleukin-18 (IL-18), sCD40L, soluble Fas ligand (sFASL), and TNF α .

Data will be collected from the subjects' medical records for up to 2 years post-randomization to collect outcomes and adverse events.

GIB episodes will be defined by INTERMACS:

An episode of SUSPECTED INTERNAL OR EXTERNAL BLEEDING that results in 1 or more of the following:

1. Death
2. Re-operation
3. Hospitalization
4. Transfusion of red blood cells as follows:
 - During first 7 days post implant (≥ 4 units packed red blood cells within any 24-hour period in patients $\geq 50\text{kg}$ or $\geq 20\text{cc/kg}$ packed red blood cells within any 24-hour period in patients $< 50\text{kg}$)
 - After 7 days post implant (transfusion of packed red blood cells (PRBC) after 7 days following implant with the investigator recording the number of units given.)

During the 1-year study period, clinical events including GIB and other major adverse events will be recorded and evaluated on a regular basis.

DATA AND SPECIMEN BANKING

Peripheral blood collected from consented participants will be stored in refrigerators at -80C for the duration of the study. All members of the research team will have access to the specimens.

Stool samples collected from consented participants will be shipped straight to [name] laboratory for microbiome analysis and storage. All samples will receive a designated study code. This code will be linked to the patient's data.

All samples, blood and stool, will be stored indefinitely for future research related to heart failure, GI bleeding, Omega-3 supplements, and microbiome.

STUDY TIMELINES

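### The Background promises results on angiopoietin-1 (Ang-1), but the assay lists leave it out, so neither Ang-1 nor the Ang-1/Ang-2 ratio can be reported as planned

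*Combined protocol and SAP*

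**What the plan says.** The last sentence of the Background commits the trial to "investigate the effect of O3FA on angiogenesis parameters (Ang-1, Ang-2, VEGF", with TNF-α as the fourth parameter.

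Earlier, the Background explains why Ang-1 matters. It says that "Ang-1 leads to normal angiogenesis in conjunction with VEG-F, while Ang-2 promotes dysfunctional vessel growth", and that "an abnormal ratio of Ang-1 and Ang-2 has a key role in abnormal angiogenesis", with Ang-2 too high and Ang-1 too low. It adds that TNF-α "contributes to abnormal angiogenesis by killing pericytes and reducing Ang-1 levels".

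The Study Endpoints section follows directly after the sentence naming the four parameters: "The primary endpoint will be a change in angiogenesis markers resulting in dysregulated angiogenesis, as described above". Aim 1 is equally general, asking whether omega-3 "alters markers of angiogenesis and inflammation in patients with continuous-flow left ventricular assist devices". Neither the endpoint nor Aim 1 names Ang-1 or the ratio.

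Blood Collection sets out the assays: "The angiogenesis factors to be measured are angiopoietin-2, epidermal growth factor (EGF), endoglin, sCD40L, vascular endothelial growth factor A, C and D", then PlGF, HB-EGF, PAI-1, IGFBP-1, TGF-α and uPA. A second list gives six inflammatory markers. Procedures Involved schedules "Collect blood sample" at baseline, 3 months, 6 months and 1 year.

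**The concern.** A parameter that the protocol says it will investigate has no planned measurement. Ang-1 is also one of the two components of the imbalance that the Background describes, and lowering it is one of the two routes given there for the action of TNF-α.

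If the assay list is followed, the trial can say whether omega-3 changed Ang-2. It cannot say whether omega-3 changed Ang-1 or moved the balance between the two.

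The omission may also touch the primary endpoint, which defines its markers only by referring back to earlier text. The most natural reading is that this text is the account of abnormal angiogenesis and the list of four parameters just before the endpoint. The wording is ambiguous, however, and the conflict between the two sections does not depend on that reading.

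**Working it through.** No figure in the plan depends on this point, so the check compares the lists and then counts.

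**1. What is to be measured (Blood Collection)**

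- Angiogenesis list, 13 analytes: angiopoietin-2, EGF, endoglin, sCD40L, VEGF-A, VEGF-C, VEGF-D, PlGF, HB-EGF, PAI-1, IGFBP-1, TGF-α, uPA.
- Inflammatory list, 6 analytes: IL-6, IL-8, IL-18, sCD40L, sFASL, TNF-α.
- Distinct analytes: 13 + 6 − 1 = 18, because sCD40L is on both lists.
- Routine tests: metabolic panel with liver function, blood count, lipids, hs-CRP, ESR.

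**2. Promised against measured**

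| Parameter named at the end of the Background | In the Blood Collection lists? |
|---|---|
| Ang-1 | No |
| Ang-2 | Yes |
| VEGF | Yes (A, C and D) |
| TNF-α | Yes (as an inflammatory marker) |

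Three of the four are covered. The list is not introduced as a set of examples, and the sentence shows no gap or redaction that could hide a missing item.

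**3. Why Ang-2 cannot stand in for the ratio**

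log(Ang-1/Ang-2) = log(Ang-1) − log(Ang-2), so

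change in log ratio = change in log(Ang-1) − change in log(Ang-2).

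Only the second term would be observed. A fall in Ang-2 is compatible with a rise, no change or a fall in the ratio, depending on the unmeasured Ang-1. Of the two shifts in the Background (Ang-2 up, Ang-1 down), only one would be seen, and this is so at all four draws.

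**4. What is not affected**

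The two Background results that tie marker levels to bleeding rest on Ang-2 alone (more nonsurgical bleeding above the mean) and on Ang-2 with TNF-α (69% against 38%, p = 0.02). Both markers are on the panel. The sample size is also untouched: an effect size of 0.8 with two-sided α of 0.05 and power of 0.8 gives 25.52 per group by the two-sample t-test, which rounds up to the plan's 26.

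**5. What adding Ang-1 and the ratio would do to multiplicity**

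The statistical section compares omega-3 with control within each of two prevention arms, at 0.05, with no adjustment. With no true effect, expected chance positives = number of tests × 0.05.

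| Markers counted | Tests per time point | Chance positives | Tests over three post-baseline draws | Chance positives |
|---|---|---|---|---|
| Panel now: 18 × 2 | 36 | 1.8 | 108 | 5.4 |
| Plus Ang-1 and ratio: 20 × 2 | 40 | 2.0 | 120 | 6.0 |
| Panel with hs-CRP and ESR: 20 × 2 | 40 | 2.0 | 120 | 6.0 |
| The same plus Ang-1 and ratio: 22 × 2 | 44 | 2.2 | 132 | 6.6 |

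**6. Assay volume**

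120 patients × 4 draws = 480 samples at most, assuming full enrolment and no losses.

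**The case against.** The strongest reply is that the gap may be recoverable. Data and Specimen Banking keeps blood without a time limit for later research on topics that would cover an Ang-1 assay, so the accurate word might be unplanned rather than impossible. This stands in part, and it makes a repair more feasible. But that storage serves future research and not a listed analysis of this trial, and the protocol does not say how much blood remains after the panel. An Ang-1 assay chosen later would fall outside the written plan.

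Second, the ratio is rationale only and is never named as an outcome. That is correct: the direct contradiction concerns one analyte. Reporting the ratio is a recommendation that follows from the Background's own mechanism.

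Third, the link to the primary endpoint is uncertain. The protocol's other mention of dysregulated angiogenesis introduces the ACE inhibitor and ARB evidence, where the marker discussed is Ang-2. This also stands, and the endpoint link should carry little weight.

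Fourth, the cost is not documented. The protocol does not say whether the multiplex system carries Ang-1, and a separate assay could cost more than one added analyte.

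None of this removes the conflict between the stated parameters and the assay list.

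**Conclusion.** The point holds. The Background and Blood Collection disagree about Ang-1, and nothing else in the protocol resolves it. If the assay list is followed, one of four named parameters and the Ang-1/Ang-2 ratio cannot be reported from the planned assays at any of the four draws. The other three parameters can be.

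Confidence is high for the conflict itself, which needs no assumption beyond reading the assay list as closed. The bearing on the primary endpoint is a reading of ambiguous wording. The defect should be corrected because a named parameter would otherwise go unmeasured, but it does not invalidate the other marker comparisons or the bleeding results.

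**What to change.** Reconcile the two sections in one of two ways.

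- **Add the assay.** Put angiopoietin-1 on the Blood Collection list, run it on the study blood from baseline, 3, 6 and 12 months, and report Ang-1 and the Ang-1/Ang-2 ratio with the other angiogenesis markers.
- **Withdraw the promise.** If Ang-1 cannot be assayed, remove it from the parameters named at the end of the Background, keep the endpoint on the angiogenesis markers that Blood Collection lists, and draw no conclusion about Ang-1 or the ratio.

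Either way, state which earlier text the primary endpoint refers back to. A minor tidy-up is to assign sCD40L (on both lists) and TNF-α (an angiogenesis parameter in the Background, an inflammatory marker in Blood Collection) to one endpoint group each. This changes only their primary or secondary label, since all markers are tested in the same way at 0.05.

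The first route costs reagents for one more analyte on at most 480 samples. The price is not in the documents. It is assumed small, and would be higher if the multiplex system does not carry Ang-1. Enough blood must also remain after the panel. No extra visit, draw or patient is needed. The statistical downside is two more outcomes, which adds 0.2 expected chance positives per time point, or 0.6 over three post-baseline draws. The second route costs only a text change, but gives up any statement about the imbalance that motivates the trial.

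### GI bleeding, a secondary endpoint, is assessed open-label under a definition that a suspected-bleed admission satisfies, with no masked classification and no analysis limited to less discretionary events

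*Combined protocol and SAP*

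**What the plan says.** Design (Procedures Involved): "We will perform an open-label, prospective, randomized control study in which 120 CF-LVAD patients are enrolled". Under Objectives, patients in both prevention populations are "randomized to high-dose O3FA or none", so there is no placebo. Each prevention arm compares 30 patients with 30.

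Role of bleeding (Study Endpoints): the primary endpoint is a change in angiogenesis markers. "Secondary endpoints include rate of GIB and improvement in inflammatory markers". Bleeding is also Aim 3 and the question in the title.

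Event definition (Blood Collection, attributed to INTERMACS): "An episode of SUSPECTED INTERNAL OR EXTERNAL BLEEDING that results in 1 or more of the following". Four outcomes follow: death, re-operation, hospitalization and red-cell transfusion. Any one is enough. Beyond the first week after implant the transfusion criterion reads "transfusion of packed red blood cells (PRBC) after 7 days following implant with the investigator recording the number of units given", with no minimum number of units.

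Ascertainment (same section): "During the 1-year study period, clinical events including GIB and other major adverse events will be recorded and evaluated on a regular basis". No assessor is named. In the visit schedule, adverse events are recorded at the same visits at which O3FA subjects alone have a "Study drug compliance check".

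Analysis (Statistical Analysis section): bleeding rates are compared between groups within each arm by unpaired t-test or Mann-Whitney U, two-sided at 0.05. There is no sensitivity analysis for bleeding.

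**The concern.** Two judgements lie between a patient's condition and a counted event: whether to admit, and whether to call the cause a suspected bleed. In an open-label trial with an untreated control group, the patient and the treating clinicians know the allocation when both are made. The Background reports the investigators' own retrospective cohort as favouring O3FA, so an expectation of benefit is on record. If controls are admitted a little more readily, or their admissions are labelled as bleeding a little more often, the comparison tilts towards O3FA. Randomization does not protect against outcome assessment that differs by group, and a single between-group test on the full definition cannot show it.

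At stake is the credibility of the Aim 3 result, which readers will take as the answer to the title. The angiogenesis markers come from a multiplex immunoassay and do not depend on these judgements.

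**Working it through.** **1. The plan's own figure.** With a standardized effect of 0.8, two-sided alpha 0.05 and power 0.8, the normal approximation gives 2 × (1.960 + 0.842)² / 0.8² = 24.5, so 25 per group. The exact two-sample t calculation gives 25.52, so 26 per group (power 80.7%), and 4 × 26 = 104. The stated figure reproduces. It is set in standardized units and is not tied to a bleeding rate.

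**2. Search for masking.** The event definition, the ascertainment sentence, the visit schedule and the statistical section contain no masked review, no adjudication and no restricted analysis. The coding of data and specimens in the statistical section is there for confidentiality; nothing links it to how events are judged.

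**3. Illustration on patients with any bleed.** Inputs: 1-year event-free rates of 97% and 79% (Background), hence 3% and 21% with an event; 30 per group (Procedures Involved). Assumptions: the outcome is yes/no and each patient counts once. The plan does not state this.

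Expected patients with a bleed: 30 × 0.03 = 0.9 and 30 × 0.21 = 6.3, about 1 versus 6.

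Mann-Whitney on a 0/1 outcome, with *a* and *b* events, n = 30 per group and N = 60:
- Distance of U from its null mean: n(b − a)/2.
- Variance: (n²/12) × [(N + 1) − Σ(t³ − t)/(N(N − 1))], where the tie groups t are the numbers with and without a bleed.
- z = (distance − 0.5)/SD, with continuity correction.

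For 1 versus 6, the distance is 75 and the ties are 7 and 53. Then Σ = 336 + 148,824 = 149,160, and 149,160/3,540 = 42.14. The variance is 75 × (61 − 42.14) = 1,414.8, SD 37.61, z = 74.5/37.61 = 1.981.

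| O3FA vs control | Distance | SD | z | Mann-Whitney p | Without correction | Fisher p |
|---|---|---|---|---|---|---|
| 1 vs 5 | 60 | 35.15 | 1.693 | 0.091 | 0.088 | 0.195 |
| 1 vs 6 | 75 | 37.61 | 1.981 | 0.048 | 0.046 | 0.103 |
| 2 vs 6 | 60 | 39.83 | 1.494 | 0.135 | 0.132 | 0.254 |

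Under Fisher's test the 0.05 boundary lies between 1 vs 7 (0.052) and 1 vs 8 (0.026).

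**4. The same endpoint as an event rate.** The Background gives 0.077 (SD 0.419) and 0.305 (SD 0.847) events per year. At 30 per group the standard error is √[(0.419² + 0.847²)/30] = 0.1725, t = 0.228/0.1725 = 1.32 on 58 degrees of freedom, p = 0.19. On this form the expected result is not near the boundary.

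**5. What a labelling bias would do if present.** The documents give no figure, so the share is assumed. Suppose the true risk is 21% in both groups and 20%, 30% or 50% of O3FA bleeds go uncounted. Summing binomial probabilities over all 30 versus 30 outcomes, the two-sided Mann-Whitney false-positive rate rises from 4.9% to 6.8%, 9.6% or 20.1%.

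**The case against.** The strongest reply has four parts.

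*The definition is the INTERMACS one and bleeding is secondary.* Both are true. The definition should stay, and the primary endpoint is not exposed. Neither fact supplies masked classification.

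*No sentence says who judges bleeds.* This stands. A reader might infer that the protocol assigns the task to unmasked staff. It does not; it is silent. What can be said is that no masked step is described in a trial declared open-label.

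*Single-event fragility is not evidence of bias.* This also stands. A reader might infer from 0.048 against 0.091 that knowledge of allocation can decide the bleeding result through one admission. The documents do not support that. Any small trial with an expected count near a threshold behaves this way, masked or not. The pattern also depends on the yes/no outcome and the Mann-Whitney test: one extra control patient beyond 1 versus 6 still leaves Fisher at 0.052, and the event-rate form gives 0.19. The documents do not say which prevention arm the 3% versus 21% describes, and they give no rate for the secondary prevention arm.

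*A restricted analysis keeps some discretion.* Correct. After the first week any red-cell transfusion qualifies, those ordering it can know the allocation, and every criterion still requires a suspected bleed. The restriction removes episodes that rest on admission alone. It reduces the problem without curing it.

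**Conclusion.** The point holds as a gap in the assessment and analysis of a secondary endpoint. An open-label comparison against no treatment, an event definition that an admission for a suspected bleed satisfies, no described masked classification and no restricted analysis together leave Aim 3 open to differential admission or labelling that the planned comparison could not reveal.

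The size of any bias is unknown. The p-values show small-sample fragility under stated assumptions, and the false-positive rates rest on assumed shares of uncounted bleeds; neither measures bias in this trial. Nothing here calls the biomarker primary endpoint into question. The change is worth making because it is cheap, and because it lets the report show whether a bleeding benefit depends on episodes counted for admission alone.

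**What to change.** 1. In the Statistical Analysis section, pre-specify a sensitivity analysis of GI bleeding limited to episodes meeting criterion 1 (death), 2 (re-operation) or 4 (red-cell transfusion). Report it beside the full definition, within each prevention arm, with estimates and confidence intervals. State in advance that a benefit seen only under the full definition will be described as not robust to open-label assessment.

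2. In the bleeding definition under Blood Collection, where existing staff allow, have a team member who is not treating the patient classify each candidate episode from coded records with allocation, O3FA entries and compliance data removed.

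3. State in the report that neither step removes bias in the decision to admit or to transfuse.

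Cost: one further analysis using outcomes and transfused units the plan already has recorded, provided the case report form captures which criterion each episode met (its contents are not in the documents). There is some record preparation, for few episodes at the expected counts. The restricted analysis will have fewer events and wider intervals. Sample size and clinical care are unchanged.
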